# 5.2. Exclusion Criteria

- 1. Diagnosis of acute promyelocytic leukemia (APML or t(15;17) PML-RARA fusion). Patients with biphenotypic disease are excluded.
- 2. Active central nervous system involvement or disorder:
  - a. Participants with a history of CNS disease are permitted to enroll if they have previously received appropriate therapy and CNS remission has been

documented and are symptom/progression free and off therapies that are controlling symptoms for at least 4 weeks prior to enrollment. **Note:** In the absence of CNS symptoms, a lumbar puncture is not required for study entry.

- Active CNS disorder, such as seizure, cerebrovascular ischemia/hemorrhage, dementia, cerebellar disease, or any autoimmune disease with CNS involvement, unless considered stable and well-controlled with ongoing treatment
- 3. Immediate life-threatening, severe complications of leukemia (sepsis, hemorrhage).
- 4. Participants with extramedullary disease as the sole site of AML
- 5. Active severe or uncontrolled infection, known human immunodeficiency virus infection, or presence of hepatitis B surface antigen (HBsAg) or positive hepatitis C antibody test at screening. **Note:** Participants with positive hepatitis C antibody due to prior resolved disease can be enrolled only if a confirmatory negative hepatitis C RNA polymerase chain reaction (PCR) (or comparable test) is obtained.
- 6. Participants with signs/symptoms suggestive of COVID-19 within 14 days of study entry, or with known exposure to COVID-19 within 14 days prior to study entry
- 7. Active autoimmune disease that has required systemic disease modifying or immunosuppressive treatment within the last 2 years.
- Concurrent medical condition requiring the use of systemic immunosuppressive treatment within 28 days before the first dose of study treatment.
   Note: Physiologic doses of corticosteroids for treatment of endocrinopathies or steroids with minimal systemic absorption, including topical, inhaled, or intranasal corticosteroids may be continued if the participant is on a stable dose.
- 9. History of vasculitis at any time prior to study treatment.
- 10. Participant has a history of other malignancies less than 2 years prior to study entry, with the exception of:
  - Adequately treated in situ carcinoma of the cervix uteri or carcinoma in situ of breast;
  - Basal cell carcinoma of the skin or localized squamous cell carcinoma of the skin;
- 11. QTcF >450 msec for male participants, >470 msec for female participants, or >480 msec for participants with bundle branch block. QTcF is QT corrected for

heart rate according to Fridericia's formula and can be machine calculated or manually over-read.

- 12. Recent history of allergen desensitization therapy within 4 weeks of starting study treatment.
- 13. History or evidence of cardiovascular (CV) risk including any of the following:
  - Clinically significant uncontrolled hypertension
  - Recent (within the past 6 months) history of serious uncontrolled cardiac arrhythmia or clinically significant ECG abnormalities including second degree (Type II) or third-degree atrioventricular block.
  - Cardiomyopathy, myocardial infarction, acute coronary syndromes (including unstable angina pectoris), coronary angioplasty, stenting, or bypass grafting within the past 6 months before enrollment.
  - Congestive heart failure (Class II, III, or IV) as defined by the New York Heart Association functional classification system [NYHA, 1994].
  - History of immune myocarditis or pericarditis.
- 14. Prior STING therapy.
- 15. Prior solid organ transplantation.
- 16. Recent prior therapy defined as follows:
  - Any non-monoclonal anti-cancer therapy within 14 days or 5 half-lives, whichever is longer, prior to start of study treatment
  - Prior therapy with biological agents (including monoclonal antibodies) within 28 days prior to start of study treatment
  - Any radiotherapy or major surgery within 14 days prior to start of study treatment
  - Currently receiving investigational therapy in a clinical trial

**Note:** Hydroxyurea may be used prior to and throughout study to control white cell count.

17. Receipt of any live vaccine within 30 days of start of study treatment. Inactivated vaccines such as the inactivated flu intramuscular vaccine are permitted. Live attenuated vaccines including herpes zoster, nasal flu, and coronavirus vaccines should be avoided. Recombinant human or non-human primate adenoviral vector vaccines are also excluded.

- 18. Immune-related toxicity related to prior treatment that has not resolved to Grade ≤1 (except alopecia, hearing loss or Grade ≤2 neuropathy or endocrinopathy managed with replacement therapy).
- 19. Concomitant administration of drugs that are sensitive substrates or narrow therapeutic range substrates for cytochrome p450 (CYP)3A4 enzyme, P-gp, BCRP, OATP1B1 and OATP1B3 transporter, and moderate to strong inducers and inhibitors of CYP3A4, P-gp, OATP1B1 and OATP1B3 should be excluded during the study and for 7 days prior to and following treatment with GSK3745417 (14 days for itraconazole). Note: any medications (including antibacterials, antifungals, and antivirals) which are necessary for the health, well-being, or standard clinical care of patients with hematologic malignancies are exempt from this restriction. Any medications potentially interacting with GSK3745417 will require a pause in GSK3745417 dosing unless allowed through consultation with Sponsor.
- 20. Ongoing drug or alcohol abuse.

# 5.3. Lifestyle Considerations

## 5.3.1. Meals and Dietary Restrictions

• Refrain from consumption of red wine, Seville oranges, grapefruit or grapefruit juice, pomelos, exotic citrus fruits, grapefruit hybrids, or fruit juices from at least 7 days before the start of study intervention until after the final dose.

# 5.3.2. Caffeine, Alcohol, and Tobacco

- During each dosing session, participants will abstain from ingesting caffeine- or xanthine-containing products (e.g., coffee, tea, cola drinks, and chocolate) for 4 hours before the start of dosing until after collection of the final PK and/or pharmacodynamic sample.
- During each dosing session, participants will abstain from alcohol for 24 hours before the start of dosing until after collection of the final PK and/or pharmacodynamic sample.
- Participants who use tobacco products will be instructed that use of nicotine-containing products (including nicotine patches and other delivery devices such as vaporizers) will not be permitted while they are in the clinical unit.

# 5.3.3. Activity

• Participants will abstain from strenuous exercise for 8 hours before each blood collection for clinical laboratory tests. Participants may participate in light recreational activities during studies (e.g., watching television, reading).

# 5.4. Screen Failures

Screen failures are defined as participants who consent to participate in the clinical study but are not subsequently entered in the study. A minimal set of screen failure information is required to ensure transparent reporting of screen failure participants to meet the Consolidated Standards of Reporting Trials (CONSORT) publishing requirements and to respond to queries from regulatory authorities. Minimal information includes demography, screen failure details, eligibility criteria, any protocol deviations, and any serious adverse events (SAEs).

Individuals identified as Screen Failures may be rescreened once if the failure was based on elements of eligibility that may change, e.g., laboratory test results.

# 6. STUDY INTERVENTION(S) AND CONCOMITANT THERAPY

Study intervention is defined as any investigational intervention(s), marketed product(s), placebo, or medical device(s) intended to be administered to a study participant according to the study protocol.

# 6.1. Study Intervention(s) Administered

GSK3745417 will be administered to participants at each study site under medical supervision of an investigator or designee. Cytokine-related AEs including changes in vital signs may begin within several hours of administration of GSK3745417. Participants must be monitored in the clinic/hospital throughout dosing in the initial cycles and for up to 24 hours after administration of the Q1W or Q3W maintenance doses, or longer as clinically indicated. Guidelines for monitoring cytokine-related AEs and tumor lysis syndrome are summarized in Section 6.4.

For Part 1, the dosing schedule each Cycle from 1 - 3 is 5 days on / 2 days off / 5 days on followed by observation for 2 weeks. After 3 cycles, participants will move to a dosing schedule of once every week (Q1W). For Part 2, after the induction regimen determined from Part 1, participants will enter a maintenance phase at a dose and schedule determined by emerging FIH data.

The specific time of study treatment administration (e.g., time of the week for first administration; time of the day for each administration) should take into consideration PK sampling time points and study visit procedures and will be recorded in the source documents and in the eCRF.

ARM NameInterventionIntervention NameGSK3745417TypeDrugDose FormulationTo be provided in the study reference manualDosage FormPowder for Solution for InjectionUnit Dose Strength(s)2 mg/vial

Weekly dosing may be done  $\pm 24$  hours and Q3W dosing may be done  $\pm 72$  hours.

Dosage Level(s)	12.5 µg – 800 µg (to be determined)		
Route of Administration	IV injection through a central or PICC line		
Use	experimental		
IMP and NIMP	GSK3745417		
Sourcing	Provided centrally by the Sponsor		
Packaging and Labeling	Study Intervention will be provided as 1 vial in a carton. Each vial and carton will be labeled as required per country requirement.		
Current/Former Name(s) or Alias(es)	N/A		

# 6.2. Preparation/Handling/Storage/Accountability

- 1. The investigator or designee must confirm appropriate temperature conditions have been maintained during transit for all study intervention received and any discrepancies are reported and resolved before use of the study intervention.
- 2. Only participants enrolled in the study may receive study intervention and only authorized site staff may supply or administer study intervention. All study interventions must be stored in a secure, environmentally controlled, and monitored (manual or automated) area in accordance with the labeled storage conditions with access limited to the investigator and authorized site staff.
- 3. The investigator, institution, or the head of the medical institution (where applicable) is responsible for study intervention accountability, reconciliation, and record maintenance (i.e., receipt, reconciliation, and final disposition records).
- 4. Further guidance and information for the final disposition of unused study intervention are provided in the Study Reference Manual.
- Under normal conditions of handling and administration, study intervention is not expected to pose significant safety risks to site staff. Take adequate precautions to avoid direct eye or skin contact and the generation of aerosols or mists. In the case of unintentional occupational exposure notify the monitor, Medical Monitor and/or GSK study contact.
- A Material Safety Data Sheet (MSDS)/equivalent document describing occupational hazards and recommended handling precautions either will be provided to the investigator, where this is required by local laws, or is available upon request from GSK.

Precaution will be taken to avoid direct contact with the study intervention. A Material Safety Data Sheet (MSDS)/equivalent document describing occupational hazards and recommended handling precautions either will be provided to the investigator, where this is required by local laws, or is available upon request from GSK. In the case of unintentional occupational exposure notify the monitor, Medical Monitor and/or GSK study contact.

## 6.3. Measures to Minimize Bias: Randomization and Blinding

This is an open-label study. Investigators and study team will have direct access to individual participant's study intervention. All screened participants will be identified by a unique participant number that will remain consistent for the duration of the study.

In Part 1, at least 3 participants will be enrolled at a particular dose level. For the first cohort, the first participant will be enrolled, treated with 10 planned doses, and observed for 2 more days before subsequent participants are enrolled into that cohort to allow assessment of initial safety data. The next 2 participants in the first cohort will receive study treatment at least 5 days apart. Study Intervention Compliance

- When the individual dose for a participant is prepared from a bulk supply, the preparation of the dose will be confirmed by a second member of the study site staff.
- When participants are dosed at the site, they will receive study intervention directly from the investigator or designee, under medical supervision. The date and time of each dose administered in the clinic will be recorded in the source documents. The dose of study intervention and study participant identification will be confirmed at the time of dosing by a member of the study site staff other than the person administering the study intervention.

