# **Overall Design and Brief Summary:**

This is a Phase 1, open label, dose escalation study to evaluate safety, pharmacokinetics, and pharmacodynamics of intravenous GSK3745417 in participants with relapsed or refractory AML or high risk MDS.

The study will be conducted in a staged approach consisting of 2 parts. Part 1 will evaluate a dosing schedule of a 5 days on/2 days off schedule for 2 weeks, and then have an additional 2 weeks off dose for observation for a total of 28 days in each cycle (5/2)/5q28d). Once a maximum tolerated dose (MTD) has been established, additional cohorts may be opened to refine dosing frequency optimization. Each cohort will include at least 3 participants and dosing of participants entering the study will be staggered by at least 5 days from D1 of previous patient for the first cohort only. Part 1 will include intra-patient dose escalation for 3 cycles, according to safety and tolerability parameters. The starting dose for Cycle 1 will be escalated in the next dose-escalation cohort until a cohort level starting dose-based MTD is reached. Individual patients may titrate above the starting dose-based MTD based on tolerability. Dose escalation cohorts will start with Cycle 1 at 12.5 µg GSK3745417. Within a cohort for an individual subject the dose may double for Cycle 2, and double again for Cycle 3 based on individual tolerability. The starting dose of subsequent cohorts will increase by 2-fold from Cycle 1 of the previous cohort. Patients may be dose reduced for subsequent cycles if there is lack of tolerability in the previous cycle (Section 6.4). The DLT period will be 28 days starting at Day 1 of Cycle 1 of each cohort. After 3 induction cycles, if a complete response (CR) or partial

response (PR) (IWG) is observed (See Appendix 9) each patient will continue with maintenance weekly dosing at the Cycle 3 dose level until disease progression or unacceptable toxicity. Participants with progressive disease after 3 induction cycles will be withdrawn from study. Participants with stable disease or PR after 3 cycles might receive additional cycles if the assessment by the investigator determined a benefit and GSK Medical Monitor agrees.

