# CONFIDENTIAL

DE Cohort	Screeningª	Cycle (Induction Period)			Follov (post-fin adminis	w-Up al dose stered)	
Study Procedure		Intervent (In-P	tion Period atient)	Observation Period (Outpatient)	TDV⁵	Follow- Up	Notes
Week	≤4	1	- 2	3 - 4	+4		
Day	≤28	-1	1 - 13	14 - 28	+30d		
Urinalysis⁰	x		Х		Х		Sample collection times: Days 1, 8 and 13 of each cycle. If urinalysis is abnormal, a microscopy should be performed.
Coagulation	x		х				Sample collection times: at screening and prior to administration of first dose of GSK3745417 and at Day 8 of each cycle. Additional coagulation samples should be collected in the event of CRS (see Section 6.4.1.4)
Study Intervention	•						· · ·
Administer GSK3745417			X				GSK3745417 will be administered the same dose within each cycle on Days 1 – 5 and Days 8 - 12 QD. Participants will receive up to 3 cycles of treatment before moving to Q1W or Q3W dosing (Section 6.1). See Section 4.1 for maximum duration of study intervention. See Section 4.1 for safety and tolerability parameters to be reviewed prior to each daily dose
Non-Azole Antifungal		х	Х	Х			Non-azole antifungals should be administered if indicated, per local standard, on Day -1 through Day 28 of each cycle.
Tumor Lysis Syndrome Prophylaxis		x					All participants should receive tumor lysis syndrome (TLS) prophylaxis prior to date of first dose of each cycle on Day -1 according to institutional guidelines (e.g., participants should receive IV fluids ± allopurinol and consider alkalization of urine and

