### Part 1

Part 1 will evaluate a dosing schedule of a 5 days on/2 days off schedule for 2 weeks, and then have an additional 2 weeks off dose for observation for a total of 28 days in each cycle (5/2/5 q28d). Once an MTD has been established, additional cohorts may be opened to refine dosing frequency optimization. Each cohort will include at least

3 participants. Part 1 will include intra-patient dose escalation for 3 cycles, according to safety and tolerability parameters. The starting dose for Cycle 1 will be escalated in the next dose escalation cohort until a cohort level MTD is reached. The first participant at the starting dose level(s) of each cohort will begin treatment after review of safety data and DEM to allow assessment of initial safety data before beginning the next participant's treatment. The dosing of subsequent participants will be staggered by  $\geq 5$  days.

Day	-1	1	2	3	4	5	6	7	8	9	10	11	12	13	14-28
GSK3745417		Х	Х	Х	Х	Х			Х	Х	Х	Х	Х		
In-patient	Х	Х	Х	Х	Х	Х	Х	Х	Х	Х	Х	Х	Х	Х	
Non-azole antifungal	Х	Х	Х	Х	Х	Х	Х	Х	Х	Х	Х	Х	Х	Х	Х

Table 6	Dosing and Hospitalization Schedule for Cycles 1 - 3

Dose escalation will initiate with Cycle 1 at 12.5 µg GSK3745417 as the first cohort and the Cycle 1 dose will increase by 2-fold between cycles (3 dose levels). The starting dose of subsequent cohorts will increase by 2-fold from Cycle 1 of the previous cohort. Patients may be dose reduced for subsequent cycles if there is lack of tolerability in the previous cycle (Section 6.4). The DLT period will be 28 days starting at Day 1 of Cycle 1 of each cohort. After 3 induction cycles, if a CR or PR (IWG) is observed (See Appendix 9), each patient will continue with maintenance weekly dosing at the Cycle 3 dose level until disease progression or unacceptable toxicity. Participants with progressive disease after 3 induction cycles will be withdrawn from study. Participants with stable disease or PR after 3 cycles might receive additional cycles if the assessment by the investigator determined a benefit and GSK Medical Monitor agrees.

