In Part 1, participants will receive dosing in the hospital on a 5 days on/2 days off schedule for 2 weeks, and then have an additional 2 weeks off dose for observation. The participant will be observed for at least 24 hours after the final dose in each cycle. All participants will be hospitalized the day before a new dosing cycle starts to receive tumor lysis syndrome (TLS) prophylaxis in line with institutional guidelines (all participants should receive IV fluids  $\pm$  allopurinol as well as alkalinization of urine with renal consult if this is in line with institutional guidance). TLS prophylaxis will continue alongside daily dosing as clinically indicated. To further reduce the risk of TLS, guidance in Section 6.4.1.2 must be followed to determine when daily dosing should be held.

Additional cohorts TBD based on emerging data

209809

\* Patients in C3 dose level in all cohorts will be continuing dosing Q1W at C3 dose level

### Part 2

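### The Part 1 staggering rules contradict each other on whether later cohorts are staggered at all and, in the first cohort, on when participant 2 may start

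*Protocol*

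**What the plan says.** Three places in the protocol set out how Part 1 participants are spaced.

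- **Section 1.1, Overall Design and Brief Summary:** "dosing of participants entering the study will be staggered by at least 5 days from D1 of previous patient for the first cohort only".
- **Section 4.1, Part 1:** "The first participant at the starting dose level(s) of each cohort will begin treatment after review of safety data and DEM". The sentence goes on to give the purpose, which is to look at initial safety data before the next participant is treated. It then continues: "The dosing of subsequent participants will be staggered by" 5 days or more. No duration is attached to the review, and the stagger is not limited to the first cohort.
- **Section 6.3:** the first-cohort rule is that "the first participant will be enrolled, treated with 10 planned doses, and observed for 2 more days before subsequent participants are enrolled into that cohort". After that, "The next 2 participants in the first cohort will receive study treatment at least 5 days apart". Nothing is said about later cohorts.

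A fourth place, the risk table (Section 2.3.1, Table 5), names staggering as a mitigation for cytokine release syndrome (CRS) but gives neither a duration nor the cohorts it covers. The SAP's account of the Part 1 design (Section 1.2) contains no stagger rule.

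**The concern.** A stagger lets the investigators see how one participant tolerates the drug before another is exposed. The protocol relies on it as a CRS safeguard, so a site needs to know which participants it applies to and how long it lasts. As written, the answer depends on the section consulted.

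The protocol's own reasoning makes both disagreements matter. Starting doses double from one cohort to the next (Section 4.1), so later cohorts begin at higher exposure, and those are the cohorts for which the stagger is in doubt. Section 4.4.2 notes preliminary non-clinical evidence that cytokine-related effects may accumulate with daily dosing. It is therefore material whether the second block of five doses has been seen before participant 2 starts.

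There is also a reporting consequence. SAP Section 6.1.3 requires important protocol deviations to be listed. A start that one section permits and another forbids cannot be classified consistently.

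**Working it through.** The protocol states no single sentinel interval to reproduce, so the check is calendar arithmetic on the dosing days, followed by a comparison of scope.

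**Inputs**

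- Dosing days, Table 1: "GSK3745417 will be administered the same dose within each cycle on Days 1 – 5 and Days 8 - 12 QD". That is 5 + 5 = 10 doses, the tenth on Day 12.
- Admission, Section 4.1: "All participants will be hospitalized the day before a new dosing cycle starts".
- Gaps and scope: the three sections cited above.
- Assumption: participant 1 has no held or missed doses.

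**First cohort, synopsis rule**

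- Earliest Day 1 for participant 2 = participant 1's Day 1 + 5 = Day 6.
- Doses participant 1 has received before Day 6: Days 1 to 5, so 5 of 10.
- Earliest Day 1 for participant 3 = Day 6 + 5 = Day 11. Before that day participant 1 has been dosed on Days 1 to 5 and 8 to 10, so 8 of 10.

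**First cohort, Section 6.3 rule**

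- End of the observation period = Day 12 + 2 = Day 14.
- Earliest Day 1 for participant 2 depends on how the boundary is read:
  - Day 14, if starting on the second observed day is allowed: gap 14 − 1 = 13 days.
  - Day 15, if Day 14 must be complete: gap 15 − 1 = 14 days.
  - Day 16, if the pre-dose admission must also follow a complete Day 14: gap 16 − 1 = 15 days.
- Doses participant 1 has received: 10 of 10 in every case.
- Earliest Day 1 for participant 3 = Day 14 + 5 = Day 19, or Day 15 + 5 = Day 20 (Day 21 on the strictest reading).

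The trigger also differs. The synopsis and Section 4.1 space dosing, whereas Section 6.3 holds back enrolment.

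**Scope, side by side**

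| | First cohort, participant 1 to 2 | Later cohorts |
|---|---|---|
| Section 1.1 | at least 5 days | no stagger required |
| Section 4.1 | safety review of unstated length; at least 5 days for subsequent participants | the same |
| Section 6.3 | 10 doses plus 2 days (about 13 to 14 days or more) | not stated |

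For a later cohort of three, the stagger in Section 4.1 puts participant 3 no earlier than participant 1's Day 11 (1 + 5 + 5). The synopsis rule would not prevent all three starting on the same day.

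**The case against.** The strongest reply is that the 5-day figures are minimums. In the first cohort, a gap of about 14 days after participant 1, followed by gaps of at least 5 days, complies with all three sections. Section 4.1 also has the same two-step shape as Section 6.3: the first participant is assessed, then the others are spaced. The two can be read together. This stands, and it rules out a stronger reading that a reader might infer, namely that there are three mutually incompatible rules.

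A second tempting inference is that every cohort faces a choice between 5 and about 14 days. It does not. The 10-doses-plus-2-days rule is expressly for the first cohort, so for later cohorts the question is whether any stagger applies.

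It can also be said that a synopsis only summarises and the body should prevail. The protocol does not say so. The first-cohort limit is also not a shortening of Section 4.1; it is a restriction that Section 4.1 does not contain. A site that staggers later cohorts anyway would break no rule, but the sections still disagree on whether it must.

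Finally, SAP Section 4.8 records that the study was terminated just as Part 1 finished recruiting. New wording cannot alter how any participant was spaced. That limits the practical effect without making the text consistent.

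**Conclusion.** The point holds in two parts.

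1. **Later cohorts.** This is the cleaner contradiction: Section 1.1 confines the stagger to the first cohort and Section 4.1 does not. The required minimum is either none or 5 days.
2. **First cohort.** A start by participant 2 on participant 1's Day 6 is allowed by the synopsis and barred by Section 6.3. The minimum gap is 5 days with 5 of 10 doses seen, or about 13 to 14 days or more with 10 of 10 seen. The shortfall is 8 days on the most lenient reading of Section 6.3 (13 − 5), 9 on the middle one (14 − 5) and 10 on the strictest (15 − 5).

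These figures assume no held doses. The documents do not show which rule the sites applied, so it would be wrong to infer that any participant was in fact started too early. The inconsistency changes no sample size or other statistical operating figure. Its weight lies in a listed safety measure that can be followed in one section and breached in another.

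**What to change.** Reconcile Sections 1.1, 4.1 and 6.3, and align Table 5, so that one rule states:

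- the gap between the first and second participant;
- the gap between later participants;
- whether each gap runs from enrolment or from dosing;
- which cohorts are covered.

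The Section 4.1 sentence on the first participant also needs rewriting. Taken literally, it makes that participant's own start conditional on the review, although its stated purpose concerns the next participant. Which rule to adopt is a clinical decision for the sponsor and investigators, and this review takes no position on it.

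Because Part 1 recruitment is complete, the useful step now is in reporting. The clinical study report should state which staggering rule was applied, by cohort, and the deviation listing under SAP Section 6.1.3 should be assessed against that rule.

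The cost is small: a few sentences in the report and a check of first-dose and enrolment dates. If the protocol itself were amended, the change is one of wording, but Section 10.1.1 requires ethics committee approval before any amended study design is implemented.
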